3.7 EFFICACY ASSESSMENT

A detailed medical history will be obtained for each subject which will include documentation of HPV-6 and/or HPV-11 RRP, a list of RRP surgeries and therapies occurring within 3 years prior to screening, and any periods of remission. Subjects must have had at least two surgical RRP interventions (including laser) in the year prior to and including Day 0, to be eligible for the study. Subjects must require RRP intervention at the time of entry into this study and will undergo surgical removal of their papilloma(s) during screening, within 14 days prior to Day 0 dosing, to maximize standardization of baseline staging across subjects.

The efficacy assessment will be based upon the number of RRP surgical interventions in the 52 weeks post Day 0 compared to the number of RRP surgical interventions in

the year prior to Day 0 dosing. RRP surgical interventions include laser therapies. The trial will also evaluate changes in RRP Staging Assessment over time as a secondary endpoint.

3.8 SAFETY ASSESSMENT

Subjects will be followed for safety from the time of signing informed consent through Week 52, or the subject's last visit. All adverse events including SAEs, UADEs, and DLTs. Clinically significant changes in laboratory parameters and vital signs from baseline assessments will be assessed.

3.9 IMMUNOGENICITY ASSESSMENT

The study will explore [REDACTED] cell mediated immune responses in blood samples taken at baseline (i.e. Screening and Day 0 prior to dosing) and Weeks 6, 9, 11, 26, and 52. Tissue samples will be collected at baseline and if clinically indicated during the study.

[REDACTED]

[REDACTED]

[REDACTED]

[REDACTED]

4.0 CLINICAL TRIAL POPULATION

4.1 INCLUSION CRITERIA

1. Provide written IRB-approved informed consent in accordance with institutional guidelines;
2. Be ≥ 18 years of age on the day of signing the informed consent, and able and willing to comply with all trial procedures;
3. Have histologically documented HPV-6- or HPV-11-positive respiratory papilloma or documentation of low-risk positive HPV using a Sponsor approved HPV-6/11 type-specific assay;
4. Have a requirement for frequent RRP intervention in order to remove or resect respiratory papilloma, as defined as at least two RRP surgical (including laser) interventions in the year prior to and including Day 0;
5. Must be appropriate candidate for upcoming surgical intervention per investigator judgement and RRP Staging Assessment score (see [Section 6.4.5](#));
6. Have adequate bone marrow, hepatic, and renal function as defined by: ANC (Absolute Neutrophil Count) ≥ 1000 cells/mm³, platelets $\geq 50,000$ /mm³, hemoglobin ≥ 9 g/dL; concentrations of total serum bilirubin within 1.5 x upper limit of normal (ULN), AST and ALT within 1.5 x ULN, serum creatinine ≤ 1.5 x ULN;
7. Agree that during the trial, male participants will not father a child, and female participants cannot be or become pregnant if they are of child-bearing potential. Subjects must meet one of the below requirements:

- a. Be of non-childbearing potential (≥ 12 months of non-therapy-induced amenorrhea, confirmed by follicle stimulating hormone [FSH], if not on hormone replacement;
- b. Be surgically sterile (vasectomy in males or absence of ovaries and/or uterus in females);
- c. Agree to use one highly effective or combined contraceptive methods that result in a failure rate of $< 1\%$ per year during the treatment period and at least through week 12 after last dose. Periodic abstinence (e.g., calendar, ovulation, symptothermal, or post-ovulation methods) and withdrawal are not acceptable methods of contraception.
- d. Agree to abstinence from penile-vaginal intercourse, when this is the subject's preferred and usual lifestyle.

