1.0 INTRODUCTION

1.1 BACKGROUND AND SCIENTIFIC RATIONALE: RRP

Human papilloma virus (HPV)-associated malignancies are an emerging global epidemic [1]. The role of HPV-6 and -11 in the etiology of recurrent respiratory papillomatosis (RRP), the most common benign tumor(s) of the laryngeal epithelium, is well-established [2, 3]. RRP is rare, with an incidence estimated at 1.8 per 100,000 adults in the United States [4], and age of diagnosis ranging from young children to older adults. Although most lesions are benign, some undergo malignant transformation, and patients with RRP have a higher risk of developing laryngeal carcinomas [5].

HPV-6 and -11 RRP-associated lesions can occur in the oropharynx, larynx, and upper respiratory tract and the clinical course of RRP varies amongst affected individuals. Selection of treatment, including active monitoring without treatment, surgery, adjuvant therapy, or a combination, depends on clinical history and expected clinical course. Repeated surgical removal of papillomas for symptomatic management remains the mainstay of treatment and results in significant morbidity considering the number of surgical procedures required, impact on voice, effects of repetitive anesthesia, psychological impact, etc [6]. Rarely, malignant transformation may occur, which is usually associated with a dismal prognosis. A few such patients with malignant disease may be candidates for salvage therapies, including potentially definitive surgery [7, 8]. Selected patients in this setting may benefit from radiation although the morbidity of this approach is substantial [8]. Recently, a Phase 2 study of pembrolizumab in patients with RRP demonstrated a response rate of 43%, and this observation supports a rationale for immunotherapeutic management of RRP [9].

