- Treatment-related NCI Common Terminology Criteria for Adverse Events (CTCAE, version 5.0) Grade ≥ 3 non-hematological toxicity that does not respond to supportive therapy and lasts for longer than 48 hours, or;

- Treatment-related NCI CTCAE v5.0 Grade ≥ 3 hematological toxicity that does not respond to supportive therapy and lasts for longer than 48 hours.

Additionally, enrollment and additional dosing will be paused until Sponsor discussion with the site Investigator determines that enrollment and dosing may continue, if the following CTCAE v5.0 events occur at any time in the study:

- One Grade 4 or 5 related SAE;
- Two Grade 3 related SAEs

Subjects will undergo routine surgical procedure for removal of papilloma(s) during the screening period within 14 days prior to Day 0 dosing (papilloma removal and Day 0 dose may be performed same day if other eligibility criteria have been fulfilled). Biopsy tissue will be collected and sent to [REDACTED] for evaluation of secondary [REDACTED] endpoints. Archival tissue (slides or blocks) obtained within one year of the screening window may be used, or a biopsy conducted during routine surgery.

Status of disease during the trial will be monitored by the Investigator during laryngoscopy including documentation with Staging Assessment scores. If at any time during the trial, surgical removal (including laser) of papilloma is clinically indicated per PI judgement, the subject may undergo procedure for papilloma removal but this must be captured on the electronic case report form. Documentation of the Staging Assessment score prior to surgery is required, and explanation for requirement of surgical removal of papilloma must be documented.

Surgical interventions during the trial must be documented to include at a minimum, information about the appearance and location of tissue being removed and instruments used. Video/photographic documentation of laryngoscopy is required.

This trial will not utilize a Data Safety Monitoring Board. This is a single-arm, open-label trial. The Sponsor will have access to unblinded safety and tolerability data during the trial. At a minimum, the Sponsor's Medical Monitor will review reported adverse events quarterly.

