3.4 SECONDARY ENDPOINT(S)

1. Number of RRP surgical interventions in the one year following Day 0, compared to the one year prior to Day 0.
2. Changes in Staging Assessment as measured by the RRP Staging Assessment score over time.
3. Antigen-specific cellular immune responses assessed by:
 - IFN- γ secreting cells in peripheral blood mononuclear cells (PBMCs) by ELISpot
 - T cell phenotype and lytic potential in PBMCs by flow cytometry
4. Assessment of pro-inflammatory and immunosuppressive elements in resected tumor tissue, if available.
5. miRNA profile as related to the reduction in frequency of RRP surgical intervention, if possible.

[REDACTED]

- [REDACTED]
- [REDACTED]
- [REDACTED]
- [REDACTED]
- [REDACTED]
- [REDACTED]
- [REDACTED]
- [REDACTED]

[REDACTED]

- [REDACTED]
- [REDACTED]
- [REDACTED]
- [REDACTED]
- [REDACTED]
- [REDACTED]
- [REDACTED]
- [REDACTED]

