4.3.1. Efficacy Analyses

The parameters that follow will be analyzed to support the conclusions of the primary analysis. For categorical endpoints, frequency and percentages will be calculated. For continuous variables, means, medians, or changes in percentage will be summarized. Where appropriate, 95% confidence intervals will be calculated (see specific analysis discussed subsequently). Analyses will be summarized and presented by number of prior surgical interventions (≤ 2 , 3-5, and ≥ 6), [REDACTED] and overall.

.

- Secondary analyses
 - Frequency of RRP surgical interventions in the year following intervention, compared to the frequency in the year prior will be presented as median difference with 95% CI based on non-parametric methodology.
 - Percent reduction in RRP surgical intervention as a categorical variable (categories consist of percent ranges), with frequency and percentages.
 - Change in surgical interval for prior to intervention to post will be presented along with median, mean, and 95% confidence intervals.
 - Change in stage as measured by the RRP Staging Assessment. Median changes and associated 95% confidence intervals will be computed.
 - The relationship of microRNA (miRNA) profiles with frequency of surgical intervention will be described using regression analysis.

■ [REDACTED]

■ [REDACTED]

■ [REDACTED]

In addition to these tabulations, by-subject listings will be provided for all efficacy endpoints.

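### The year that qualifies a subject is also the only named comparator for surgery counts, so some fall is expected with no drug effect, most visibly in the percent-reduction table

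*Protocol*

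**What the plan says.** Protocol 4.1, criterion 4, defines the required surgical need as "at least two RRP surgical (including laser) interventions in the year prior to and including Day 0". Protocol 3.7 adds that "Subjects must require RRP intervention at the time of entry into this study", with papilloma removal no more than 14 days before dosing.

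The first secondary endpoint in Protocol 3.4 is "Number of RRP surgical interventions in the one year following Day 0, compared to the one year prior to Day 0". SAP 4.3.1 carries this through: the yearly frequency "compared to the frequency in the year prior will be presented as median difference with 95% CI based on non-parametric methodology". It also plans a table of percent reduction in categories. SAP 5 explains that the median replaces the mean fold-change of Protocol 8.5.2.1.

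Protocol 3.0 states "This is a single-arm, open-label trial". SAP 3.6 plans no covariate adjustment, and Protocol 8.3 plans no hypothesis test.

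Protocol 1.1 notes that "the clinical course of RRP varies amongst affected individuals". Protocol 3.7 collects "a list of RRP surgeries and therapies occurring within 3 years prior to screening, and any periods of remission", and Protocol 6.1.1.1 asks for the same history. No readable efficacy analysis in Protocol 8.5.2.1 or SAP 4.3.1 names that longer history as a comparator.

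**The concern.** A subject enters only if the count in one particular year reaches a threshold, and that count is then the baseline. Where yearly counts fluctuate, a year chosen for being high enough tends to be followed by a lower one. This is regression to the mean, and it needs no treatment effect. With a single arm, nothing in the readable plan separates it from a drug effect.

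The surgery count is the first-listed efficacy endpoint. The Summary of Changes from Version 2.0 to 3.0 (item 1) says the data are meant to inform Phase 3 planning. A reader of the CSR could take the whole before-after change, and in particular the share of subjects with a large percent reduction, as the drug's effect.

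**Working it through.** **Plan's own figure.** None is given for surgery counts. The only sample-size figure is the bound of under 12% on SAE incidence in SAP 3.1. The two-sided 95% Clopper-Pearson upper limit for 0 of 30 is 1 - 0.025^(1/30) = 11.6%, so it reproduces. It does not bear on this point.

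**Inputs from the documents.** The threshold is two in the year up to and including Day 0, the comparator is that same year, there is one arm, and n is about 30. The only surgery-rate information is that two pilot patients had needed surgery about every six months, that is, about 2 per year.

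**Assumptions.** No drug effect. Yearly counts are Poisson given the subject's rate. Rates are gamma with mean m of 2, 3 or 4 per year and shape k of 1.5 or 3. Extra year-to-year variation has log-SD 0 or 0.5. That gives 3 x 2 x 2 = 12 scenarios. The screening surgery is left out of both years' counts, so the figures show selection alone. If it is one of the two qualifying surgeries, one other is needed; if not, two others are needed.

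**Worked case** (m = 2, k = 3, log-SD 0). Let b = k/m = 1.5.

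- P(0) = (b/(1+b))^k = 0.6^3 = 0.216.
- P(1) = k x P(0)/(1+b) = 3 x 0.216/2.5 = 0.2592.
- Expected next-year count given a count of j is (k+j)/(b+1): 1.2 for j = 0 and 1.6 for j = 1.

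One other surgery needed:

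- Prior year: 2/(1 - 0.216) = 2.55.
- Following year: (2 - 0.216 x 1.2)/0.784 = 2.22.
- Change: -0.33 (-13%).

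Two others needed:

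- Prior year: (2 - 0.2592)/(1 - 0.216 - 0.2592) = 1.7408/0.5248 = 3.32.
- Following year: (2 - 0.2592 - 0.2592 x 1.6)/0.5248 = 1.3261/0.5248 = 2.53.
- Change: -0.79 (-24%).

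**All 12 scenarios, by simulation:**

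| With no drug effect | One other surgery needed | Two others needed |
|---|---|---|
| Mean fall | about 0.15 to 0.5 (3 to 18%) | 0.4 to 1.1 (7 to 31%) |
| Median difference | 0 in 9, -1 in 3 | -1 in all 12 |
| Subjects with a reduction of 50% or more | 25 to 45% | 27 to 52% |

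With one other surgery needed, 45 to 53% of subjects decrease and 29 to 39% increase. For n = 30, the order-statistic interval for the median (ranks 10 and 21, coverage 95.7%) lies wholly below 0 in about 0.5 to 4.5% of trials; nominal is about 2%.

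**Sensitivity to the rate.** With two others needed and a mean rate of 6 per year, the fall shrinks to 0.09 to 0.29. That run used constant rates or gamma rates of shape 1 or 2, with no extra yearly variation.

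**Older years as comparator.** In the 12 scenarios the mean of years -3 and -2 matches the post-Day 0 mean to within 0.02. This follows from assuming exchangeable years and is not evidence that they are exchangeable. If surgeries instead recur at fairly regular gaps, a fall of 0.36 to 0.47 remains against the older years, because follow-up starts just after a surgery. Averaging all three years does not solve the problem: with two others needed and mean rates of 2 to 4, a fall of 0.11 to 0.30 persists.

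**The case against.** Several points on the other side have force.

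- **The endpoint is secondary and descriptive.** This stands. The matter is interpretation, not type I error.
- **The larger figures are not the natural reading.** A reader might infer a fall of up to 31% with a median of -1. Criterion 4 counts surgeries up to and including Day 0, and the required removal falls within the 14 days before dosing or on the same day, so it most naturally is one of the two. On that reading the planned median is mostly 0 and its interval is little affected. The percent-reduction table remains exposed.
- **A reader might infer that the 3-year history is ignored.** The documents do not show that. Efficacy text is redacted in both documents, prior RRP treatment is summarised at baseline (SAP 4.2), and the change in surgical interval has no stated look-back (SAP 4.3.1). Nor do they say that every listed surgery carries a date.
- **A reader might take the older years as an unbiased baseline.** They may be lowered by treatment breaks, which the Summary of Changes from Version 2.0 to 3.0 (item 10) gives as the reason for relaxing the history requirement. They may also include adjuvant therapy, excluded only in the 3 months before Day 0 (Protocol 4.2). They cannot therefore gate an efficacy statement.

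None of this removes the overlap between the qualifying year and the comparator, or supplies a benchmark for it.

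**Conclusion.** The point holds in this form: the prior year both qualifies the subject and is the only comparator named in a readable surgery-count analysis, so part of any fall is expected without a drug effect. The mean fell in every scenario run. The size rests on assumed rates that the documents do not give. On the natural reading of criterion 4, with mean rates of 2 to 4 per year, the fall is about 0.15 to 0.5 surgeries; if two other surgeries are required it is 0.4 to 1.1. The output most at risk is the percent-reduction table, where 25 to 45% of subjects reach a 50% reduction by chance on the natural reading.

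This does not show that an observed reduction would be wholly artefact. Whether the screening surgery counts in the pre-dose year is a separate question; counting it there would add about one surgery per subject to that side only. The change is worth making because it is cheap and the estimate is meant to inform later development.

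**What to change.** In SAP 4.3.1:

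1. Add a supportive, non-gating comparison of the post-Day 0 count with each subject's annualised count over months -36 to -13, limited to time after diagnosis and to subjects with available history. Use the same median difference and percent-reduction categories. A list reaching 3 years before screening covers this window.
2. Tabulate yearly counts for years -3, -2, -1 and +1, with the number of subjects with usable history in each.
3. Flag subjects with treatment breaks or adjuvant RRP therapy in the older years, and any enrolled under the earlier three-year criterion, whose older years were also selected.
4. State in the CSR that the one-year comparison includes regression to the mean, and that the older window reduces this but may not remove all bias.

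SAP 3.12 records that the first 21 subjects have been analysed, so the addition should be dated relative to that analysis.

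The cost is SAP wording and one or two tables from history the protocol already asks for, provided surgeries can be placed by year. The downside is that older history will be incomplete and may be lowered by treatment breaks or adjuvant therapy, and the apparent benefit may look smaller.

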4.2 EXCLUSION CRITERIA

Subjects Must Not:

1. Receive therapy directed towards RRP disease (other than surgery or ablation) including but not limited to anti-virals (including cidofovir), radiation, chemotherapy, anti-angiogenic therapy (including bevacizumab), prophylactic HPV vaccination (including Gardasil) as therapeutic intervention, or therapy with an experimental agent within 3 months prior to Day 0;
2. Have ongoing or recent (within one year) evidence of autoimmune disease that required treatment with systemic immunosuppressive treatments, with the exception of: vitiligo, childhood asthma that has resolved, type 1 diabetes, residual hypothyroidism that requires only hormone replacement, or psoriasis that does not require systemic treatment;
3. Have a diagnosis of immunodeficiency or treatment with systemic immunosuppressive therapy within 28 days prior to the first dose of trial treatment, including systemic corticosteroids;
4. Have a high risk of bleeding or require the use of anti-coagulants for management of a known bleeding diathesis;
5. Receive any live virus vaccine within 4 weeks prior to first dose of trial treatment or any non-live vaccine within two weeks prior to the first dose of trial treatment;
6. Have a history of clinically significant, medically unstable disease which, in the judgment of the Investigator, would jeopardize the safety of the subject, interfere with trial assessments or endpoint evaluation, or otherwise impact the validity of the trial results. This may include chronic renal failure; myocardial ischemia or infarction; New York Heart Association (NYHA) class III/ IV cardiac disease); any cardiac pre-excitation syndromes (such as Wolff-Parkinson-White; cardiomyopathy, or clinically significant arrhythmias); current malignancy with the exception of treated basal or squamous cell skin cancers, prostate cancer, or carcinoma of the cervix in situ; HIV, which may impact the ability to mount an immune response to the study therapy; or drug or alcohol dependence;
7. Have fewer than two acceptable sites available for IM injection considering the deltoid and anterolateral quadriceps muscles. The following are unacceptable sites:
 - a. Tattoos, keloids or hypertrophic scars located within 2 cm of intended treatment site;

- b. Cardioverter-defibrillator or pacemaker (to prevent a life-threatening arrhythmia) that is located ipsilateral to the deltoid injection site (unless deemed acceptable by a cardiologist);
 - c. Metal implants or implantable medical device within the intended treatment site;
8. Be imprisoned, or compulsory detainment (involuntary incarceration) for treatment of either a psychiatric or physical (i.e. infectious disease) illness;
9. Be pregnant or current breastfeeding;
10. As determined by the Investigator, have any medical or psychological or non-medical condition that might interfere with the subject's ability to participate or affect the safety of the subject.

4.3 DISCONTINUATION/WITHDRAWAL OF CLINICAL TRIAL SUBJECTS

A subject will be considered to have completed the trial when the subject has completed all study visits through Week 52. Subjects may withdraw consent at any time for any reason or be dropped from the trial at the discretion of the Investigator should any untoward effect occur. In addition, the Investigator or the Sponsor has the right to discontinue a subject from the trial at any time.

The Investigator must notify the Sponsor within 24 hours when a subject has been discontinued/withdrawn due to an Adverse Event (AE). Any AEs and/or SAEs present at the time of discontinuation/withdrawal should be followed in accordance with the safety requirements outlined in [section 7.1: Safety Parameters](#).

4.3.1 CRITERIA FOR DISCONTINUATION OF INVESTIGATIONAL PRODUCT

A subject should not receive any further investigational product (IP) if any of the following occur:

- Subject withdrawal of consent or subject is lost to follow up
- An AE that, in the opinion of the investigator or the Sponsor, contraindicates further dosing of any trial medication
- Pregnancy
- Subject non-compliance that, in the opinion of the Investigator or Sponsor, warrants discontinuation
- Initiation of new contraindicated therapy

In the absence of any of the above criterion, if limited clinical benefit is suspected at any time, IP may be discontinued after consultation between the Investigator and the Medical Monitor.

4.3.2 CRITERIA FOR DISCONTINUATION FROM THE STUDY

All subjects should be encouraged to complete all study treatments and follow up visits. If a subject is discontinued from treatment, the subject should be encouraged to stay in the study and complete all follow-up visits and procedures and have all scheduled immune assessment blood samples collected as indicated in the Schedule of Events ([Table 1](#)). At a minimum, the Investigator should request to have the subject complete the End of Study visit assessments as indicated in the schedule of events at the subject's final visit.

